153 AP/PA correction scan = 7 min) to calculate fractional anisotropy and diffusivity in white
154 matter tracts as well as derive tract-based statistics. Cerebrovascular integrity and
155 pathology will be assessed using the following contrasts: PD/T2 = 5 min; FLAIR = 7 min,
156 and T2* = 5 min). Functional magnetic resonance imaging at rest (rsfMRI plus field map
157 = 12 min) will also be acquired to measure change in data-driven functional networks.

158 **9.5 Change in Blood biomarkers measures**

159 Serum biomarkers of inflammation (C reactive protein, and interleukin 6), neuroplasticity
160 (brain-derived neurotropic factor), endothelial health (vascular endothelial growth factor
161 1), and vitamin D serum levels will be measured before and after intervention.

162 **9.6 Covariates**

163 Pre-specified covariates will be age, sex, years of education and number of
164 comorbidities.

165

166 **10. Statistical Analysis**

167 **10.1 Descriptive Analysis**

168 The baseline characteristics will be summarized using means and standard deviation, or
169 medians and interquartile range where appropriate, for continuous characteristics, and
170 frequencies and percentages for categorical variable.

171 **10.2 Primary Efficacy Analysis**

172 The primary analysis will be based on the intention-to-treat principle, including everyone
173 who were randomized. Comparisons between arms will be conducted according to pre-
174 specifications in the protocol. These comparisons align well with the recommended
175 analysis and reporting of factorial trials⁵, which used “inside the table” and “at the
176 margin” analyses for different comparisons. The “inside the table” analysis will be used
177 to compare each intervention effect to control, while “at the margins” analysis will be
178 used to assess the effect of adding intervention.

179 The major interest would be the effect of the intervention on change in primary
180 outcomes at 6 Month compared to the control arm (arm 5). The primary outcome
181 measure of mean change in ADAS-Cog-13 and ADAS-Cog-Plus scores will be analyzed
182 using a linear mixed model with restricted likelihood estimation. The model will be fitted
183 with participant-specific random intercept and fixed effects of time, intervention arm, and
184 time x intervention arm interaction. The time variable will be used as a categorical
185 variable (0 = baseline; 1 = Month 6.) The intervention arm variable will be dummy

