186 coded, using the control group as a reference category. The interaction term will be

187 used to assess between-group differences (representing a mean difference in change in
188 cognitive scores over time between two groups). With dummy coding of the intervention
189 arm, the interaction term will allow to compare the mean change in each intervention
190 arm to the arm 5 (control). The within-group difference (representing a mean change in
191 cognitive scores over time within the group) will be measured with marginalized mean
192 from the linear mixed regression model. The model will be further adjusted for
193 participant characteristics including age, sex, education, and comorbidities.

194 An unstructured covariance matrix will be used for all models. The model assumption
195 will be assessed using the normal quantile plots of residuals for normality and the
196 residuals vs. fitted plot for variance homogeneity. If the assumptions are not fully met,
197 the data will be transformed (i.e., log). Missing data will not be imputed and will be
198 assumed to be missing at random, as the mixed model approach is well-known to
199 handle such data effectively.⁶ The baseline data from individuals who did not complete
200 Month 6 assessment will be included in the linear mixed model.

201 The mean difference between groups will be presented with their 95% CI and p-value,
202 while the mean change within group will be presented with their standard error. The
203 obtained marginalized mean and standard deviation will be used to calculate the effect
204 size (
$$\frac{\text{mean change in treatment } X - \text{mean change in treatment } Y}{\text{pooled standard deviation of change}}$$
). As outlined in our published
205 protocol, we will calculate the proportion of participants with improvement in primary
206 outcomes.

207 All tests will be two-sided, and p-value of less than 0.05 will be considered as
208 statistically significant. Adjustments for multiple comparisons will not be made as the
209 trial is intended to compare the intervention effect to the control rather than pairwise.⁷
210 Per-protocol analysis will be performed as well.

211 As per recommended analyses of fractional factorial design⁸, “at the margin” analyses
212 will be performed by collapsing arms according to the pre-specified comparison.
213 Collapsing intervention arms allow to increase the study power to detect the difference

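### The SAP adjusts the primary mixed model for four person-constant covariates but names no covariate-by-time term; read as main effects, they leave the time x arm contrast unchanged with complete data and nearly so with 15% attrition

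*Combined protocol and SAP*

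**What the plan says.** SAP 9.6 states: "Pre-specified covariates will be age, sex, years of education and number of" comorbidities. It gives no functional form.

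SAP 10.2 analyses the two primary scores "using a linear mixed model with restricted likelihood estimation", fitted "with participant-specific random intercept and fixed effects of time, intervention arm, and" their interaction. Time has two levels, baseline and Month 6. The interaction is the efficacy measure: it is "used to assess between-group differences (representing a mean difference in change in" cognitive scores. The model is then further adjusted for "participant characteristics including age, sex, education, and comorbidities".

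On covariance, the same section says: "An unstructured covariance matrix will be used for all models". Missing scores are not imputed, and the baseline data of people without the "Month 6 assessment will be included in the linear mixed model".

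Sections 10.2.1 to 10.2.4 reuse this model for the collapsed-arm and multidomain contrasts. Section 10.2.5 extends time to three levels. None of 9.6, 10.2 or 10.2.1 to 10.2.5 names a covariate-by-time term. The baseline score is an outcome row in this model and not a covariate. Protocol section 8 describes a repeated-measures ANCOVA with baseline values as covariates and mentions none of these four covariates.

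**The concern.** The efficacy contrast is a difference in within-person change. Age at entry, sex, years of education and comorbidity count take one value per person. As main effects they explain who scores higher or lower overall, and they say nothing about who changes more. To act on change they must be allowed a different coefficient at Month 6, and the SAP does not provide for that.

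Two things are at stake. First, a report that the result was unchanged after adjustment would be read as a robustness finding, when the model all but guarantees the agreement. Second, with 40 per arm, chance imbalance in age or education is plausible. If those variables predict six-month change, the adjusted analysis would leave the imbalance almost untouched and gain almost no precision.

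**Working it through.** **Inputs.** From the SAP: five arms at 1:1:1:1:1, 40 per arm, 15% attrition, d = 0.5 on change (sections 4 and 7); model terms, two-level time, REML, random intercept and unstructured covariance (section 10.2). The SAP gives no figure for the adjusted contrast, so there is none to reproduce. Means, SDs, covariate effects and dropout mechanism in the simulations below are assumptions. The complete-data identity does not depend on them.

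**1. Algebra.** For a person in arm k with covariates X:

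- Y0 = a + b_k + g'X + e0
- Y6 = a + b_k + t + d_k + g'X + e6
- D = Y6 − Y0 = t + d_k + (e6 − e0)

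X drops out of D. The regressors of D (intercept, arm) are a subset of those of Y0 (intercept, arm, X). In such a nested pair of equations, generalised least squares for the smaller equation equals ordinary least squares under any 2 x 2 covariance. So the estimate of d_k is the mean change in arm k minus the mean change in arm 5, with or without X. This covers both the random intercept and the unstructured covariance.

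**2. Complete data, 200 of 200, REML.** Contrasts of arms 1 to 4 against arm 5:

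| Model | Arm 1 | Arm 2 | Arm 3 | Arm 4 | SE |
|---|---|---|---|---|---|
| Raw difference in mean change | −2.499139 | −0.995074 | −2.443951 | −2.014003 | |
| Unadjusted | −2.499139 | −0.995074 | −2.443951 | −2.014003 | 0.842447 |
| Covariate main effects | −2.499139 | −0.995074 | −2.443951 | −2.014003 | 0.842447 |
| Covariates x time added | −2.410 | −0.984 | −2.409 | −2.041 | 0.850–0.860 |

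Both covariance structures gave the same figures. In a second data set age was made to predict change (assumed 0.3 points per year). The unadjusted and main-effect contrasts were again identical (−1.384, −1.134, −1.020, 0.027; SE 1.010). Covariate-by-time terms moved them to −1.271, −1.413, −1.171 and −0.592, with SE about 0.947.

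**3. About 15% missing at Month 6, dropout depending on age and baseline score (assumed).** The identity is no longer exact, because participants lacking Month 6 contribute baseline rows through which the covariates enter. Over 60 runs in each of four scenarios (age effect absent or present, two covariance structures), main-effect adjustment shifted a contrast with SD 0.07 to 0.13 points, at most 0.38, against an SE of about 1.0. The SE changed by less than 1% on average. A separate simulation with other assumed values gave a shift SD of 0.05 against an SE of about 0.70.

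**4. What interactions could gain.** Let R² be the share of change variance that the four covariates explain. The documents do not give it. The SE is multiplied by √(1 − R²). For arms 1–4 against arm 5 with 40 × 0.85 = 34 completers per arm (136 against 34):

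Variance factor: 1/34 + 1/136 = 1.25/34.

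Power = Φ(0.5 / √(1.25/34 × (1 − R²)) − 1.96)

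| Assumed R² | SE reduction | Power |
|---|---|---|
| 0 | 0% | 74% |
| 0.05 | 2.5% | 76% |
| 0.10 | 5% | 78% |
| 0.15 | 8% | 81% |

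This formula ignores the small SE cost of the extra terms, so the powers are upper figures. The first data set shows that cost: the SE rose from 0.842 to between 0.850 and 0.860, or 1 to 2%.

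**The case against.** The strongest reply is that the SAP never says the covariates are main effects only. It says the model is adjusted and lists names. That is correct, and the point rests on the natural reading: the SAP writes out the one interaction it wants and no other. If covariate-by-time terms are already intended, the SAP still has to say so.

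A second reply is that nothing here invalidates the trial. This stands. Allocation is randomised, the unadjusted contrast is unbiased with complete data, and its confidence interval already allows for chance imbalance. The defect touches only the added adjustment step.

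Third, the precision gain depends on how well the covariates predict change. This also stands: with no predictive value the gain is nil, and the SE rises slightly.

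A reader might go further and infer that the adjustment does nothing at all in this trial. The documents do not support that. The SAP plans for 15% attrition and keeps non-completers' baseline rows, so the covariates do enter the likelihood and the estimate moves a little.

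**Conclusion.** The point holds in a limited form. As SAP 10.2 naturally reads, covariate adjustment leaves the time x arm contrast and its SE exactly unchanged with complete data. With about 15% missing at Month 6 it moves the contrast by roughly a tenth of an SE (SD 0.07 to 0.13 points against about 1.0, under assumed simulation values). The same applies to the collapsed-arm contrasts in 10.2.1 to 10.2.3, the multidomain contrast in 10.2.4 and the changes from baseline in 10.2.5.

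The main harm is interpretive: agreement between adjusted and unadjusted results would carry almost no information about robustness. The loss of precision is secondary and conditional on an unknown R². It would be wrong to conclude that the primary result is biased or that the trial's inference fails. The covariates also do real work on the arm main effect, that is, on baseline differences, but that is not the efficacy measure.

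**What to change.** In SAP 10.2 to 10.2.5, replace the adjustment sentence with one stating that the model includes age, sex, years of education and number of comorbidities together with their interactions with visit, continuous covariates being centred. State whether the adjusted or the unadjusted model is primary.

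The cost is a short SAP edit and no new data. It uses 4 × 1 = 4 extra degrees of freedom in the two-visit models and 4 × 2 = 8 in the three-visit model of 10.2.5. If the covariates turn out not to predict change, the SE may rise by a percent or two.

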APPENDIX I

Procedure	Visit 1 Screening	Visit 2 Baseline	Randomization	Visit Table		
				Visit 3 6M Visit	Telephone Follow-up (9M post-Baseline)	Visit 4 12M Visit
Written Informed Consent	X					
Demographic Information	X					
PASE Questionnaire	X			X		X
Mini Mental State Examination (MMSE)	X					
Montreal Cognitive Assessment (MoCA) Logical Memory 1 & 2 *	X			X		X
CERAD Word List Recall *						
Geriatric Depression Scale (GDS-30)	X			X		X
Generalized Anxiety Disorder 7 (GAD-7)	X			X		X
Clinical Dementia Rating (CDR)	X			X		X
Physical Activity Readiness Questionnaire Plus (PAR-Q +)	X					
ADCS-ADL and IADL	X			X		X
Clinical Medical Questionnaire		X		X		X
Dual Task Control Assessment		X		X		X
Six Minute Walk Test (6MWT) ^		X		X		X
Quality of Life Questionnaire (SF-36)		X		X		X
ADAS-Cog 13 (+ tests **)		X		X		X
Digit Span Forward and Backward WAIS-III **		X		X		X
TMT A and B **		X		X		X
Digit Symbol Test **		X		X		X
Boston Naming Test **		X		X		X
Colour Word Interference Test		X		X		X
Envelope Test		X		X		X
Short Physical Performance Battery (SPPB)		X		X		X
Gait Assessment using Gait Mat and accelerometers (when available)		X		X		X
Neuroimaging (MRI)		X		X		
Blood Draw		X		X		X
Falls Calendar ^^		X		X	X	X

* These tests are implemented to harmonize with inclusion criteria for COMPASS-ND and are not mandatory if the MoCA score ≤ 24 .

** Testing included in the ADAS Cog Plus.

^ 6MWT can be completed at the Baseline Visit or at Day 1 of intervention sessions at the gymfacilities. Please note date and location of the 6MWT in patient file.

^^ Calendar will be given to participant to complete and will be submitted to Research Staff at exercise training.

1
2
3
4
5
6
7

Statistical Analysis Plan (SAP)

10
11
12
13 **SYNchronizing Exercises, Remedies in Galt and Cognition (SYNERGIC) Trial**

13 SYNchronizing Exercises, Remedies in Galt and Cognition (SYNERGIC) Trial

14
15
16
17
18
19
20
21
22
23

Version: Final

Authors: [name], PhD, University of Western Ontario
[name](c), University of Western Ontario
[name], Parkwood Institute
[name], University of Western Ontario and Robarts Research Institute
[name], University of Western Ontario

Date: Sept 2022

24
25
26
27
28
29
30

31 1. Introduction

32 The SYNERGIC TRIAL (SYNchronizing Exercises, Remedies in Galt and Cognition) is
33 a randomized, phase II, fractional factorial, five-arm, double-blind controlled study
34 evaluating the effect of aerobic-resistance exercise with and without cognitive training

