35 and vitamin D supplementation on cognitive function.

36 Specifically, physical exercise is a progressive and supervised aerobic (AE) and
37 resistance training (RT) program tailored for older adults' physical capabilities.
38 Computerized cognitive training will be delivered using the Neuropeak cognitive training
39 program designed to target working memory and attention. Vitamin D supplementation
40 will be delivered in capsules with 10,000 IU, 3 times per week, reaching a weekly dose
41 of 30000 IU. Control interventions will be sham cognitive training, balance and toning
42 exercise (BAT), and matching vitamin D placebo capsules.

43

44 2. Study Objectives

45 To evaluate:

46 **Objective 1** The effect of supervised aerobic-resistance exercise on cognitive function

47 **Hypothesis 1.** Twenty weeks of supervised aerobic-resistance exercise will significantly
48 improve cognitive function in older adults with MCI, as assessed by primary outcome
49 Alzheimer's Disease Assessment Scale-Cognitive (ADAS-Cog 13 and plus variant) and
50 secondary outcomes, compared to a balance and toning (BAT) control.

51 **Objective 2.** The effect of adding cognitive training to aerobic-resistance exercise on
52 cognitive function.

53 **Hypothesis 2.** Adding cognitive training to aerobic-resistance exercise will significantly
54 improve primary and secondary outcomes compared to aerobic-resistance exercise
55 without cognitive training.

56 **Objective 3.** The effect of adding vitamin D supplementation to aerobic-resistance
57 exercise on cognitive function.

58 **Hypothesis 3.** Adding vitamin D supplementation in weekly dose of 30000 IU to
59 aerobic-resistance exercise will significantly improve primary and secondary outcomes
60 compared to aerobic-resistance exercise without vitamin D supplementation.

61 **Objective 4.** The effect of multi-domain intervention (aerobic-resistance exercise +
62 cognitive training + Vitamin D supplementation) on cognitive function.

63 **Hypothesis 4.** The multi-domain intervention (aerobic-resistance exercise + cognitive
64 training + vitamin D supplementation) will significantly improve primary and secondary
65 outcomes compared to the control intervention.

66

67 3. Study Population

68 We will target older adults aged 60 to 85 years old with mild cognitive impairment (MCI).

69

70 4. Study Design

71 This is a Phase II, randomized, double-blind, five-arm controlled trial. The trial design

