 72 follows a fractional factorial design as shown in Figure 1. Participants will be recruited
 73 primarily from the community and from clinics serving MCI population across five sites:
 74 London (lead and sponsor site), Waterloo-University of Waterloo, Waterloo-Wilfrid
 75 Laurier University, Montreal, and Vancouver. All eligible participants will be randomized
 76 to 5 arms in 1:1:1:1:1 ratio:

[figure not shown]
77 Arm 1: combined AE and RT exercise + cognitive training + vitamin D

78 Arm 2: combined AE and RT exercise + cognitive training + placebo vitamin D

79 Arm 3: combined AE and RT exercise + control cognitive training + vitamin D

80 Arm 4: combined AE and RT exercise + control cognitive training+ placebo vitamin D

81 Arm 5: BAT exercise + control cognitive training + placebo vitamin D

82 AE: aerobic exercise; RT: progressive resistance training; BAT: balance and toning control

83 Figure 1. Trial design overview

84 5. Study Endpoint

85 The study endpoint will be at 6 Month (post-intervention).

86

87

6. Study Assessment

88 The participant's eligibility will be assessed during the screening visit. Assessment
 89 which will be performed during three visits: baseline, post-intervention at 6 months, and
 90 6-month follow up after the postintervention at 12 months. The measures at each
 91 assessment are described in Table 1.

92

93 Table 1. Assessments across study visits

Procedure	Visit 1 Screening	Visit 2 Baseline	Visit 3 6 month	Telephone Follow-up at 9 month	Visit 4 12 month
Written Informed Consent	X				
Demographic Information	X				
Mini Mental State Examination (MMSE)	X				
Physical Activity Readiness Questionnaire Plus (PARQ +)	X				
Logical Memory 1 & 2	X				
CERAD Word List Recall	X				
PASE Questionnaire	X				
Montreal Cognitive Assessment (MoCA)	X		X		X
Generalized Anxiety Disorder 7 (GAD-7)	X		X		X
Geriatric Depression Scale (GDS-30)	X		X		X
Clinical Dementia Rating (CDR)	X		X		X
Activities of Daily Living (ADCS-ADL and IADL)	X		X		X
Clinical Medical Questionnaire		X	X		X
Dual Task Control Assessment		X	X		X
ADAS-Cog 13 (+ tests ^a)		X	X		X
Trail Making Test A & B ^a		X	X		X
Digit Symbol Test ^a		X	X		X
Digit Span Forward and Backward WAIS-III ^a		X	X		X
Boston Naming Test ^a		X	X		X
Verbal Fluency Test ^a		X	X		X
Colour Word Interference Test		X	X		X
Quality of Life Questionnaire (SF-36)		X	X		X
Short Physical Performance Battery (SPPB)		X	X		X
Gait Assessment using Gait Mats and accelerometers (when available)		X	X		X

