214 in effect. More details are provided below for each pre-specified comparison.

215 10.2.1 Effect of aerobic-resistance exercise

216 To address objective 1 (the effect of supervised aerobic-resistance exercise on
217 cognitive function), the intervention arms providing exercise intervention (arm 1 to 4) will
218 be collapsed as one category and compared to the control (arm 5). The new
219 independent variable will be created to represent exercise intervention: aerobic-
220 resistance exercise intervention (collapsed arm 1 to 4), and control exercise intervention
221 – BAT – (arm 5). The new intervention variable will be fitted into the same linear mixed
222 model described above. Using the interaction between exercise intervention x time, the

223 change in primary outcome will be contrasted between participants receiving the
224 aerobic-resistance exercise and those not receiving the aerobic-resistance exercise.

225 10.2.2 Effect of adding cognitive training

226 The objective 2 (the effect of adding cognitive training to aerobic-resistance exercise on
227 cognitive function) will be examined by pooling the intervention arms providing both
228 exercise and cognitive intervention (arm 1 and 2) and pooling the intervention arms
229 providing exercise intervention but not cognitive intervention (arm 3 and 4). A new
230 independent variable will be created for addition of cognitive training: both exercise and
231 cognitive intervention (pooled arm 1 and 2) and exercise but no cognitive intervention
232 (pooled arm 3 and 4). Using the interaction term in the linear mixed model, the contrast
233 will be made between the two collapsed arms to assess whether the effect of adding
234 cognitive training to aerobic-resistance exercise differ from aerobic-resistance exercise.
235 If there is a significant difference observed, the two collapsed arms will be compared to
236 the control arm (arm 5). This marginal analysis will allow to evaluate the main effect of
237 aerobic-resistance exercise alone (pooled arm 1 and 2) and aerobic-resistance exercise
238 with cognitive training (pooled arm 3 and 4) compared to the control (arm 5) with higher
239 power (as a result of increase in sample size).^{5,8}

240 10.2.3 Effect of adding vitamin D supplements

241 The objective 2 (the effect of adding vitamin D to aerobic-resistance exercise on
242 cognitive function) will be examined by pooling the intervention arms providing both

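### The contrast that the SAP labels the effect of exercise (arms 1-4 against arm 5) also carries half of each add-on's effect, and no text ties an exercise-alone conclusion to arm 4 against arm 5

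*Combined protocol and SAP*

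**What the plan says.** SAP section 1 describes the trial as "evaluating the effect of aerobic-resistance exercise with and without cognitive training" and vitamin D, and protocol sections 2.1.a and 3 frame the question in the same way. SAP section 2 then drops the qualifier. Objective 1 is "The effect of supervised aerobic-resistance exercise on cognitive function", and Hypothesis 1 begins "Twenty weeks of supervised aerobic-resistance exercise will significantly", with the balance-and-toning control as comparator and no add-on mentioned.

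Section 10.2.1 takes Objective 1 and says that the four exercise arms will "be collapsed as one category and compared to the control (arm 5"). Its last sentence reads the result as people who received the exercise against people who did not. Section 10.2 authorises the pooling in general: the margin analyses "will be performed by collapsing arms according to the pre-specified comparison".

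Two arms differ only in exercise (SAP section 4): "Arm 4: combined AE and RT exercise + control cognitive training+ placebo vitamin D" and "Arm 5: BAT exercise + control cognitive training + placebo vitamin D". Section 10.2 does produce that comparison. It explains that once dummies code the intervention "arm, the interaction term will allow to compare the mean change in each intervention" arm with arm 5, and it reports such differences with a 95% CI and p-value. Of these single-arm contrasts, only arm 1 against arm 5 is assigned to an objective (10.2.4). The SAP speaks of exercise alone once, in 10.2.2, and attaches it to pooled arms 1 and 2, which are the cognitive-training arms.

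**The concern.** In a complete factorial, the add-ons would be spread equally over active and control exercise and would cancel from the exercise margin. Here no arm gives cognitive training or vitamin D without exercise. The add-ons appear on one side of the 10.2.1 contrast only and are confounded with exercise.

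The pooling is not the error: it answers the programme question in SAP section 1. The error is the label and the reading given to it. If the SAP is followed as written, a significant pooled result stands as an effect of exercise even when some or all of it comes from the add-ons. The SAP also does not say what may be concluded about exercise when the pooled contrast is significant and arm 4 against arm 5 is not.

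**Working it through.** **Estimand.** Let E be the effect of exercise alone (arm 4 minus arm 5), CT and D the effects of adding each component to exercise, and I their interaction. Relative to arm 5 the arm means are:

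- Arm 1: E + CT + D + I
- Arm 2: E + CT
- Arm 3: E + D
- Arm 4: E

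Allocation is 1:1:1:1:1 (SAP section 4), so the pooled contrast is (4E + 2CT + 2D + I)/4 = **E + CT/2 + D/2 + I/4**. It equals E only when CT/2 + D/2 + I/4 = 0. In 10.2.2, arms 3 and 4 against arm 5 gives (2E + D)/2 = E + D/2, so that pool is not exercise alone either.

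**The plan's own power figure.** SAP section 7 gives 80% power at d of about 0.5 with 40 per arm, and says that 15% attrition is accounted for. With a two-sided 0.05 t-test, arms 1-4 against arm 5 at 160 vs 40 gives 80.4%. With 34 completers per arm (40 × 0.85), 136 vs 34 gives 73.7%. The 80% is thus reached for this contrast only without attrition. The labelling point does not depend on this.

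**Precision with 34 per arm, in SD of change.**

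- Pooled contrast: SE = √(1/136 + 1/34) = 0.192; power at 0.5 is 73.7%.
- Arm 4 against arm 5: SE = √(2/34) = 0.243; power at 0.5 is 52.9% on 66 df, or 53.6% with the five-arm residual (165 df).

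**How often the label misleads.** The documents give no component effects, so those below are assumptions, from 0.2 SD up to the SAP's own 0.5. The simulation takes one outcome, E = 0, 34 per arm and 400,000 runs per row. The pooled test uses 168 df, arm 4 against arm 5 uses 165 df, and the margin tests are 68 vs 68. Column (a) is pooled significant. Column (b) is pooled significant and arm 4 against arm 5 not. Column (c) is as (b), with neither the 10.2.2 nor the 10.2.3 margin test significant.

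| CT, D, I | (a) % | (b) % | (c) % |
|---|---|---|---|
| 0, 0, 0 | 5.0 | 2.9 | 2.6 |
| 0.2, 0, 0 | 8.0 | 5.7 | 4.2 |
| 0.2, 0.2, 0 | 17.5 | 15.1 | 8.9 |
| 0.5, 0, 0 | 23.8 | 21.4 | 3.1 |
| 0.5, 0.25, 0 | 46.8 | 44.3 | 5.0 |
| 0.5, 0.5, 0 | 70.4 | 67.9 | 1.9 |
| 0.2, 0.2, -0.2 | 12.1 | 9.8 | 7.9 |
| 0.5, 0.5, -0.5 | 47.8 | 45.3 | 21.7 |
| 0.2, 0.2, +0.2 | 24.3 | 21.9 | 7.0 |
| 0.5, 0.5, +0.5 | 85.4 | 82.7 | 0.0 |

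Arm 4 against arm 5 is significant in 5% throughout, as it should be when E = 0.

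**The case against.** The best defence has four parts.

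1. **The SAP already gives the right comparison.** Section 10.2 assigns intervention-against-control comparisons to the inside-the-table analysis, names comparison with arm 5 as its major interest, and keeps the margins for the effect of adding a component. Arm 4 against arm 5 is therefore a planned contrast. This is true, but it also shows 10.2.1 departing from that rule: Objective 1 is a comparison with control and is answered with a margin. Still no sentence names arm 4 as the basis for exercise alone.

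2. **Objective 1 and 10.2.1 never say alone**, and 10.2.1 lists the pooled arms openly. That also stands. It makes this a fault of labelling and interpretation, not a hidden analysis.

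3. **The follow-up comparisons would expose the add-ons.** After a significant margin, 10.2.2 and 10.2.3 compare both pools with arm 5. With CT = 0.5 only, the pooled and cognitive-training tests are both significant in about 19.7% of trials, and arms 3 and 4 against arm 5 is then non-significant in 18.4% (about 93% of those). With both add-ons at 0.5 the follow-up is weaker, about 43 of 57 points. It isolates E only if the other add-on is inert, and it does not run in the cases of column (c).

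4. **Other valid estimates of E exist.** An additive model over the five arms has SE √((0.75 + 1)/34) = 0.227 against 0.243. It needs an assumption of no interaction, and the SAP does not plan it.

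It is also fair to say that every row sets E = 0, and that the 21.7% needs two effective add-ons that together do no better than one, contrary to the protocol's synergy hypothesis.

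**Conclusion.** The concern holds. The 10.2.1 contrast estimates E + CT/2 + D/2 + I/4, and the SAP's label and reading treat it as the effect of exercise. The algebra needs only the arm definitions and equal arm sizes.

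The size of the problem depends on effects that the documents do not give. If the add-ons have no net effect, the label does no harm. Under the assumptions above, large add-on effects usually show in the margin tests. A misleading pooled result goes unsignalled in about 2 to 9% of trials without interaction (2.6% by chance alone) and in up to about 22% with strong negative interaction. The signalled cases matter too, because a significant margin test does not alter what 10.2.1 says its result means. The plan should be corrected, though the pooled analysis itself is sound.

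**What to change.** 1. In Objective 1, Hypothesis 1 and section 10.2.1 (heading and last sentence), name the pooled contrast: *exercise-based programmes, with or without cognitive training and/or vitamin D, versus control*.
2. Add to 10.2.1: *Any conclusion about aerobic-resistance exercise alone rests on arm 4 versus arm 5 from the model in 10.2, reported beside the pooled contrast with its 95% CI. If the pooled contrast is significant and arm 4 versus arm 5 is not, the effect of exercise alone is reported as inconclusive.*
3. As a separate editorial correction, reverse the two pool labels in the last sentence of 10.2.2. Arms 1 and 2 are exercise with cognitive training. Arms 3 and 4 are exercise without cognitive training (with or without vitamin D). The same section defines the pools correctly earlier on.

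No new data, model or arm is needed, and the pooled contrast keeps its power for the programme question. The cost is a less precise exercise-alone conclusion. If exercise works at 0.5 SD and the add-ons do nothing, about 23% of trials would have a significant pooled result and still call exercise alone inconclusive. If both add-ons also work at 0.2 SD, this is about 42%. These rates reflect how little the design says about exercise alone; the pooled test cannot supply that information.
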